5.2 Treatment Assignment

Phase 1 of the study will be open-label and subjects will be assigned to Arms as specified in the study design ([Section 3.1](#)).

Phase 2 of the study will be open-label and randomized. Subjects (including subjects enrolled in Safety Run-in) will be randomized in a 1:1 manner to receive CRS-207/epacadostat/pembrolizumab or CRS-207/pembrolizumab.

5.3 Dose Limiting Toxicities

During Phase 1, the DLT evaluation period is defined as Cycle 1 (21 days).

During the Phase 2 Safety Run-in, the DLT evaluation period is defined as Cycle 1 (the first 21 days).

5.3.1 Non-Hematologic Events

For non-hematological events, a DLT is defined as any treatment-emergent adverse event (TEAE) not attributable to disease or disease-related processes that occurs during the DLT observation period (Cycle 1) and is Grade 3 or higher according to National Cancer Institute (NCI) Common Terminology Criteria for Adverse Events (CTCAE) v4.

In addition, any use of systemic steroids or a study drug dose interruption lasting more than 7 days for an adverse event with an unclear relationship to study drug will be considered a DLT even if the other DLT criteria are not fulfilled.

The following non-hematological adverse events are NOT considered DLTs:

- Grade 3 aspartate aminotransferase (AST), alanine aminotransferase (ALT), or alkaline phosphatase levels persisting for <7 days;
- Grade 3 fatigue lasting <3 days;
- Grade 3 nausea or vomiting that has resolved to ≤ Grade 2 within 48 hours with standard antiemetic therapies;
- Grade 3 diarrhea that has resolved to ≤ Grade 2 within 48 hours with standard antidiarrheal therapies;
- Grade 3 fever;
- Grade 3 or 4 laboratory finding that is asymptomatic and rapidly reversible (returned to baseline or ≤ Grade 1 within 7 days) unless identified as clinically significant by the Investigator;
- Any Grade 3 or lower change in cholesterol or triglycerides or asymptomatic change in lipid profile; and/or
- Singular or non-fasting elevations in blood glucose (i.e. blood glucose excursions will be considered a DLT if fasting blood glucose is elevated (Grade 3 or higher) on 2 separate occasions).

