For non-hematological events, a DLT is defined as any treatment-emergent adverse event (TEAE) not attributable to disease or disease-related processes that occurs during the DLT observation period (Cycle 1) and is Grade 3 or higher according to National Cancer Institute (NCI) Common Terminology Criteria for Adverse Events (CTCAE) v4.

In addition, any use of systemic steroids or a study drug dose interruption lasting more than 7 days for an adverse event with an unclear relationship to study drug will be considered a DLT even if the other DLT criteria are not fulfilled.

The following non-hematological adverse events are NOT considered DLTs:

- Grade 3 aspartate aminotransferase (AST), alanine aminotransferase (ALT), or alkaline phosphatase levels persisting for <7 days;
- Grade 3 fatigue lasting <3 days;
- Grade 3 nausea or vomiting that has resolved to ≤ Grade 2 within 48 hours with standard antiemetic therapies;
- Grade 3 diarrhea that has resolved to ≤ Grade 2 within 48 hours with standard antidiarrheal therapies;
- Grade 3 fever;
- Grade 3 or 4 laboratory finding that is asymptomatic and rapidly reversible (returned to baseline or ≤ Grade 1 within 7 days) unless identified as clinically significant by the Investigator;
- Any Grade 3 or lower change in cholesterol or triglycerides or asymptomatic change in lipid profile; and/or
- Singular or non-fasting elevations in blood glucose (i.e. blood glucose excursions will be considered a DLTs if fasting blood glucose is elevated (Grade 3 or higher) on 2 separate occasions).

Hematologic Events

For hematologic events, a DLT is defined as follows:

- Grade 4 neutropenia lasting >7 days;
- Grade ≥3 febrile neutropenia;
- Grade 4 anemia;
- Grade 4 thrombocytopenia or ≥ Grade 3 thrombocytopenia lasting >7 days or associated with bleeding; and/or
- Dose delay >7 days secondary to myelosuppression.

Toxicities will be monitored throughout the study, and if the toxicity levels in any Arm are unacceptable (>33% of subjects), then dosing will be suspended until further review and consideration by the SRC.

INCLUSION AND EXCLUSION CRITERIA:

Inclusion Criteria

Individuals must meet all of the following requirements to be eligible to enroll in this study:

1. Female, 18 years of age or older
2. Histologically-confirmed disease

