Treatment-emergent AEs were reported in 49 subjects (98.0%). Fatigue was the most frequently reported treatment-emergent AE (33 subjects, 66.0%) followed by rash (27 subjects, 54.0%; includes the preferred terms rash, rash generalized, rash macular, rash maculopapular, and rash pruritic). More than half of subjects (64.0%) had treatment-emergent AEs \geq grade 3 in severity.

Nineteen subjects (38.0%) had a treatment-emergent AE leading to discontinuation of epacadostat. Five of the 7 subjects (71.4%) treated in the 300 mg BID cohort, 4 of the 8 subjects (50.0%) treated in the 25 mg BID cohort, 7 of the 18 subjects (38.9%) treated in the 50 mg BID cohort, and 3 of 9 subjects (33.3%) treated in the 50 mg BID intermittent dose cohort discontinued epacadostat because of treatment-emergent AEs. No subjects in either the 100 mg BID group or the 75 mg TDD group had a treatment-emergent AE leading to discontinuation of epacadostat.

In a recent ongoing Incyte Corporation Phase 1 study (INCB 24360-202), safety, efficacy, and tolerability of the combination of pembrolizumab at a dose of 2 mg/kg IV every 3 weeks in combination with epacadostat at doses of 25 mg BID to 300 mg BID in subjects with various, advanced or metastatic solid tumors is being evaluated. A total of 60 subjects were enrolled as of 29 October 2015: 25 mg BID (n=4) and, 50 mg BID (n=20), 100 mg BID (n=18), and 300 mg BID (n=18). Preliminary results from this study showed that one grade 3 rash (8%) was reported in the 50 mg BID cohort and this was found to be DLT based on the extent of rash. The most common all grade immune-related AEs were rash (16%), diarrhea (16%), dyspnea (8%), pruritus (8%), and headache (8%). The ORR per modified RECIST v1.1 (mRECIST) was 71% (5/7), and disease control rate (DCR; CR+PR+stable disease) was 100% (7/7) (note: calculations included only evaluable subjects for response).

Based on the preliminary, unaudited data as of the data cutoff (29 Oct 2015), no Grade 4 treatment-related AEs were reported. Three subjects (5%) discontinued for a treatment-related AE: grade 3 arthralgia, grade 3 AST increased, and grade 2 nervous system disorder. No treatment-related deaths occurred. Treatment-emergent AEs were reported in 44 subjects (73.0%). The most frequently reported AEs were rash (27%) followed by fatigue (23%). Rash includes the preferred terms rash, rash generalized, rash maculopapular, rash pruritic, and rash follicular.

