Hypophysitis	2-4	Therapy with epacadostat can be continued while endocrine replacement therapy is instituted.	Related: Reduce by 1 dose level Not Related: Same dose level	Toxicity does not resolve within 12 weeks of last dose or inability to reduce corticosteroid to 10 mg or less of prednisone or equivalent per day within 12 weeks
Hyperthyroidism	3	Toxicity resolves to Grade 0-1	Related: Reduce by 1 dose level Not Related: Same dose level	Toxicity does not resolve within 12 weeks of last dose or inability to reduce corticosteroid to 10 mg or less of prednisone or equivalent per day within 12 weeks
	4	Permanently discontinue	n/a	Permanently discontinue
Hypothyroidism	1-4	Therapy with epacadostat can be continued while thyroid replacement therapy is instituted	n/a	Therapy with epacadostat can be continued while thyroid replacement therapy is instituted
Pneumonitis	2	Toxicity resolves to Grade 0-1	Related: Reduce by 1 dose level	

¹ Subjects with bone metastasis related elevations at baseline, contact sponsor to discuss clinical management and possible dose reductions of epacadostat.

² For subjects with liver metastasis who begin treatment with Grade 2 AST or ALT, if AST or ALT increases by greater than or equal to 50% relative to baseline and lasts for at least 1 week then subjects should be discontinued. For subjects have transient Grade 3 AST/ALT levels persisting for < 7 days and do NOT require steroids, epacadostat may reduce by 1 dose level once AST/ALT returns to baseline.

Toxicity	Hold Treatment For Grade	Timing for Restarting Treatment	Dose Level for Restarting Treatment	Treatment Discontinuation
			Not Related: Same dose level	Toxicity does not resolve within 12 weeks of last dose or inability to reduce corticosteroid to 10 mg or less of prednisone or equivalent per day within 12 weeks
	3-4	Permanently discontinue	n/a	Permanently discontinue
Renal Failure or Nephritis	2	Toxicity resolves to Grade 0-1	Related: Reduce by 1 dose level Not Related: Same dose level	Toxicity does not resolve within 12 weeks of last dose or inability to reduce corticosteroid to 10 mg or less of prednisone or equivalent per day within 12 weeks
	3-4	Permanently discontinue	n/a	Permanently discontinue

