All Other Drug-Related Toxicity	3 or Severe ³	Toxicity resolves to Grade 0-1	Related: Reduce by 1 dose level Not Related: Same dose level	Toxicity does not resolve within 12 weeks of last dose or inability to reduce corticosteroid to 10 mg or less of prednisone or equivalent per day within 12 weeks
	4	Permanently discontinue	n/a	Permanently discontinue

³ Subjects with intolerable or persistent Grade 2 drug-related AE may hold study medication at physician discretion. Permanently discontinue epacadostat for persistent Grade 2 adverse reactions for which treatment with study drug has been held, that do not recover to Grade 0-1 within 12 weeks of the last dose.

Table 7 Pembrolizumab Dose Modification Guidelines for Drug-Related Adverse Events

Toxicity	Hold Treatment For Grade	Timing for Restarting Treatment	Treatment Discontinuation
Diarrhea/Colitis	2-3	Toxicity resolves to Grade 0-1	Toxicity does not resolve within 12 weeks of last dose or inability to reduce corticosteroid to 10 mg or less of prednisone or equivalent per day within 12 weeks
	4	Permanently discontinue	Permanently discontinue
AST, ALT, or Increased Bilirubin	2	Toxicity resolves to Grade 0-1	Toxicity does not resolve within 12 weeks of last dose
	3-4	Permanently discontinue (see exception below) ^a	Permanently discontinue
Type 1 diabetes mellitus (if new onset) or Hyperglycemia	T1DM or 3-4	Hold pembrolizumab for new onset Type 1 diabetes mellitus or Grade 3-4 hyperglycemia associated with evidence of beta cell failure	Resume pembrolizumab when subjects are clinically and metabolically stable
Hypophysitis	2-4	Toxicity resolves to Grade 0-1. Therapy with pembrolizumab can be continued while endocrine replacement therapy is instituted	Toxicity does not resolve within 12 weeks of last dose or inability to reduce corticosteroid to 10 mg or less of prednisone or equivalent per day within 12 weeks
Hyperthyroidism	3	Toxicity resolves to Grade 0-1	Toxicity does not resolve within 12 weeks of last dose or inability to reduce corticosteroid to 10 mg or less of prednisone or equivalent per day within 12 weeks
	4	Permanently discontinue	Permanently discontinue
Hypothyroidism		Therapy with pembrolizumab can be continued while thyroid replacement therapy is instituted	Therapy with pembrolizumab can be continued while thyroid replacement therapy is instituted
Infusion Reaction	2 ^b	Toxicity resolves to Grade 0-1	Permanently discontinue if toxicity develops despite adequate premedication

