	3-4	Permanently discontinue	Permanently discontinue
Pneumonitis	2	Toxicity resolves to Grade 0-1	Toxicity does not resolve within 12 weeks of last dose or inability to reduce corticosteroid to 10 mg or less of prednisone or equivalent per day within 12 weeks
	3-4	Permanently discontinue	Permanently discontinue
Renal Failure or Nephritis	2	Toxicity resolves to Grade 0-1	Toxicity does not resolve within 12 weeks of last dose or inability to reduce corticosteroid to 10 mg or less of prednisone or equivalent per day within 12 weeks
	3-4	Permanently discontinue	Permanently discontinue
All Other Drug-Related Toxicity ^c	3 or Severe	Toxicity resolves to Grade 0-1	Toxicity does not resolve within 12 weeks of last dose or inability to reduce corticosteroid to 10 mg or less of prednisone or equivalent per day within 12 weeks
	4	Permanently discontinue	Permanently discontinue

Note: Permanently discontinue for any severe or Grade 3 (Grade 2 for pneumonitis) drug-related AE that recurs or any life-threatening event.
 
^a For subjects with liver metastasis who begin treatment with Grade 2 AST or ALT, if AST or ALT increases by greater than or equal to 50% relative to baseline and lasts for at least 1 week then subjects should be discontinued. Grade 3 AST/ALT levels persisting for < 7 days, pembrolizumab may resume once AST/ALT has returns to baseline.
 
^b If symptoms resolve within one hour of stopping drug infusion, the infusion may be restarted at 50% of the original infusion rate (e.g. from 100 mL/hr to 50 mL/hr). Otherwise dosing will be held until symptoms resolve and the subject should be pre-medicated for the next scheduled dose; Refer to Table 9 for further management details.
 
^c Subjects with intolerable or persistent Grade 2 drug-related AE may hold study medication at physician discretion. Permanently discontinue study drug for persistent Grade 2 adverse reactions for which treatment with study drug has been held, that do not recover to Grade 0-1 within 12 weeks of the last dose.
			

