5.4.3.3 Discontinuation Rules and Procedures for Immune-Related Adverse Events

Adverse events of a potential immunologic etiology or irAEs may be defined as an adverse event of unknown etiology, associated with drug exposure and consistent with an immune phenomenon. IrAEs may be predicted based on the nature of the compounds, their mechanism of action, and reported experience with immunotherapies that have a similar mechanism of action. Special attention should be paid to adverse events that may be suggestive of potential irAEs. An irAE can occur shortly after the first dose or several months after the last dose of treatment.

If an irAE is suspected, efforts should be made to rule out neoplastic, infectious, metabolic, toxin, or other etiologic causes prior to labeling an adverse event as an irAE. If other causes exist, additional supportive care may be required. Subjects who develop a \geq Grade 2 irAE should be discussed immediately with the Sponsor.

General supportive care recommendations to manage irAEs due to epacadostat are detailed in [Table 8](#). In addition, recommendations for prophylactic and supportive care measures of specific irAEs, infusion reactions, pneumonitis, hepatitis, dermatitis, immune-mediated neuropathies, immune-mediated endocrinopathies, and ocular manifestations are detailed throughout [Section 5.4](#).

irAEs may be attributable to one or more study drugs. If the event is clearly related to one of the agents, follow the instructions specific for that agent, if available. If the event is related to multiple agents, follow the action taken instructions provided, or consult the Study Medical Monitor.

Table 8 General Guidelines for Immune-Related Adverse Events Due to Epacadostat

irAE Toxicity Grade	Withhold/Discontinue Epacadostat*	Action Taken With Respect to Epacadostat	Supportive Care
Grade 1	No action.	Not applicable.	Provide symptomatic treatment.
Grade 2	May withhold epacadostat per Investigator's discretion.	May return to treatment if improves to Grade 1 or resolves within 6 weeks. If adverse event resolves within 4 weeks, subject may restart at the same dose and schedule for epacadostat. For an adverse event that does not resolve within 4 weeks, epacadostat should be reduced 1 dose level. If adverse event does not resolve within 6 weeks, study treatment with epacadostat should be discontinued or discussed with Study Medical Monitor.	Consider systemic corticosteroids in addition to appropriate symptomatic treatment.

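### Section 5.3.1 counts a hold of more than 7 days as a DLT when causality is unclear, but not when a sub-Grade 3 event is clearly drug-related (minor, wording)

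*Protocol*

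**What the plan says.** Section 5.3.1 makes a non-hematologic event in Cycle 1 a DLT if it is Grade 3 or higher and not explained by the disease. One further sentence adds "any use of systemic steroids or a study drug dose interruption lasting more than 7 days", with the hold tied to causality: a "dose interruption lasting more than 7 days for an adverse event with an unclear relationship to study drug will be considered a DLT", whether or not another criterion is met. The synopsis carries the same text.

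The list of exemptions in 5.3.1 has two entries that bear on the liver. One covers Grade 3 AST, ALT or alkaline phosphatase lasting under 7 days. The other covers any "Grade 3 or 4 laboratory finding that is asymptomatic and rapidly reversible", meaning recovery to baseline or Grade 1 or below inside 7 days, unless the Investigator judges it clinically significant.

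The dose-modification text in Section 5.4 expects holds for lower-grade related events:
- Table 6, footnote 3: "Subjects with intolerable or persistent Grade 2 drug-related AE may hold study medication at physician discretion".
- Table 8, for a Grade 2 immune-related event: "May withhold epacadostat per Investigator's discretion". Restart at the same dose is allowed if it resolves within 4 weeks, and steroids are only to be considered.

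For Grade 3-4 AST, ALT or bilirubin, Table 6 (epacadostat) and Table 7 (pembrolizumab, drug-related events) require permanent discontinuation. Their exceptions for brief elevations stop at Grade 3 AST/ALT: "transient Grade 3 AST/ALT levels persisting for < 7 days and do NOT require steroids" in Table 6, and "Grade 3 AST/ALT levels persisting for < 7 days, pembrolizumab may resume" in Table 7.

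**The concern.** A DLT should capture toxicity that the treatment causes and that interrupts dosing. As written, the hold criterion captures doubtful cases and leaves out certain ones. The laboratory exemption creates a second mismatch, because an event serious enough to end a drug permanently can still be exempt from the DLT count.

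The count that matters is mainly the Phase 2 Safety Run-in. Section 1.3.4 reports no DLT among the eight subjects given CRS-207 with epacadostat by November 2016. In the run-in, two or more DLTs in up to six subjects per arm oblige the SRC to meet about the dose (Section 3.2). Section 3.2 also says there were no earlier data on adding pembrolizumab. Hepatic enzyme changes are expected with both CRS-207 (Section 1.3.1) and epacadostat (Section 1.3.3).

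**Working it through.** The documents give no figure for DLT counting, so there is nothing to reproduce. The check is a reading of the rules, followed by simple arithmetic.

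**1. Routes to a DLT under the literal text** (non-hematologic, Cycle 1, no systemic steroids)

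| Event | Route | DLT? |
|---|---|---|
| Grade 3 or higher, not disease-related, not on the exempt list | grade | yes |
| Grade 2, relationship unclear, held >7 days | hold clause | yes |
| Grade 2, clearly drug-related, held >7 days | none | **no** |
| Grade 4 ALT, asymptomatic, Grade 1 or below inside 7 days, not called clinically significant | general laboratory exemption | **exempt** |
| Grade 3-4 bilirubin, same conditions | general laboratory exemption | **exempt** |

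**2. Does anything correct rows 3 to 5?**
- Section 5.3.2 counts a delay of more than 7 days from myelosuppression without requiring doubt about the drug's role. The qualifier therefore looks like a drafting slip and not a principle.
- Section 9.1.1 records causality only as No or Yes, so *unclear* is not a recorded category.
- No text says that the specific AST/ALT bullet overrides the general laboratory bullet, and bilirubin has no bullet of its own.
- The SAP points back to the protocol criteria (Section 3.1) and lists DLTs (Section 8.1, Listing 16.2.7.2).

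**3. How far does the steroid trigger close the gap?** Section 5.4.3.1 directs steroids for Grade 2 pneumonitis, hypophysitis, hepatic and renal events, and for Grade 2 diarrhea/colitis lasting more than 3 days. If steroid use counts on its own, those events are caught. The sentence leaves open whether the causality qualifier also applies to steroids. Section 5.4.3.1 gives no steroid instruction for rash or fatigue.

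**4. Can the events fit in the 21-day window?**
- Holds: the first missed day is Day s, and the hold exceeds 7 days on Day s + 7. From s + 7 ≤ 21, s ≤ 14. Phase 2 epacadostat starts on Day 3, so s runs from 4 to 14, which is 11 possible start days. This is mainly an issue for the epacadostat arm, since the infused drugs are given once in Cycle 1.
- Liver: Phase 2 Cycle 1 tests include Days 3 and 8 (Protocol Table 1). A Grade 4 value on Day 3 that is Grade 1 or below on Day 8 has recovered in 8 − 3 = 5 days.

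**5. Effect on the count.** 2/6 = 33.3% meets the trigger; 1/6 = 16.7% does not.

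**6. Scale, under assumptions only.** Let p be the true DLT rate and m the share uncounted, both assumed, and r = p(1 − m). Then P(2 or more of 6) = 1 − (1 − r)^6 − 6r(1 − r)^5.

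| p | m = 0 | 10% | 25% | 50% |
|---|---|---|---|---|
| 0.25 | 0.466 | 0.406 | 0.314 | 0.167 |
| 0.33 | 0.642 | 0.573 | 0.460 | 0.259 |
| 0.50 | 0.891 | 0.836 | 0.726 | 0.466 |

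The documents support no value of m.

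**The case against.** The added sentence is there to widen DLT counting. It applies even when no other criterion is met, so its likely intent is that doubt about causality should not excuse a long hold. Section 5.4.1 uses a similar phrase to introduce adverse-event interruptions in general. A sensible investigator would probably count a clearly related hold as well. This stands as a view of intent, and it is one reason the point is minor. It does not change what the text says, and a DLT definition should not depend on the reader supplying the missing half.

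The liver gap is narrow, and that also stands. The event must be asymptomatic, recover in time, be untreated with systemic steroids, and not be called clinically significant. Section 5.4.3.1 directs IV steroids for Grade 3-4 hepatic immune events, though only where epacadostat or pembrolizumab is held responsible. Section 5.4.1 requires discussion with the Study Medical Monitor, an SRC member, before dosing resumes after a liver-test hold. Permanent discontinuation might itself be read as a hold of more than 7 days, but that helps only where causality is unclear. Leaving brief laboratory changes to Investigator judgement is defensible when CRS-207 is expected to move liver enzymes. What remains is the conflict with Tables 6 and 7, whose discontinuation rule does not depend on that judgement.

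A reader might take the rash (27%) and fatigue (23%) frequencies in Section 1.1.3.3 as the size of the hold gap. They are not: they are overall frequencies from a different study, not Grade 2 events held for more than 7 days in Cycle 1 without steroids.

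**Conclusion.** The hold criterion is wrong as written, and the point is minor. Literally read, it omits clearly drug-related events below Grade 3 and includes doubtful ones. The liver point is secondary and narrower: it needs all the conditions in the last two rows of the first table under the working.

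A reader might infer that the run-in would miss unacceptable toxicity, or that its chance of triggering review is materially reduced. The documents do not support that. The share of affected events is unknown, and the probabilities above rest on assumed rates. The trigger changes no dose by itself; it convenes a committee that already reviews all adverse events and can meet at any time. The suspension rule in Section 5.3.2, at more than 33% of subjects with unacceptable toxicity, is not worded in terms of DLTs.

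Nor do the documents show that an event was in fact left uncounted. SAP Section 3.5 records that development ceased in December 2017 and that all but two subjects had finished treatment by 12 January 2018. The conclusion concerns the definition, not the results.

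**What to change.** In Section 5.3.1 and the matching synopsis text:
1. In the interruption criterion, replace the causality qualifier with *related to study drug or of unclear relationship*.
2. State separately that systemic steroid use for an adverse event in Cycle 1 is a DLT, so that the new wording does not narrow that trigger.
3. Add to the general laboratory exemption that a liver laboratory event requiring permanent discontinuation of a study drug under Table 6 or Table 7 is not exempt. Grade 3 AST/ALT lasting under 7 days stays under its own bullet. This covers bilirubin, which the tables treat in the same row.

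The cost is a wording change, and slightly more events may count as DLTs. If an amendment is no longer practical, the sponsor can flag in or beside Listing 16.2.7.2 any Cycle 1 event that would count under the clarified wording.
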